4.7.6 Discontinuation Criteria

Treatment with study drug should be permanently discontinued for the following:

- Any Grade 2 drug-related uveitis or eye pain or blurred vision that does not respond to topical therapy and does not improve to Grade 1 severity within the re-treatment period OR requires systemic treatment
- Any Grade 3 non-skin, drug-related adverse event lasting > 7 days or recurs, with the following exceptions for laboratory abnormalities, diarrhea, colitis, neurologic toxicity, drug-related uveitis, pneumonitis, bronchospasm, hypersensitivity reactions, myocarditis, infusion reactions, and endocrinopathies:

- Grade 3 drug-related diarrhea, colitis, neurologic toxicity, uveitis, pneumonitis, bronchospasm, myocarditis, hypersensitivity reaction, or infusion reaction of any duration requires discontinuation
- Grade 3 drug-related endocrinopathies, adequately controlled with only physiologic hormone replacement do not require discontinuation. Adrenal insufficiency requires discontinuation regardless of control with hormone replacement.
- Grade 3 drug-related laboratory abnormalities do not require treatment discontinuation except:
 - ◆ Grade 3 drug-related thrombocytopenia > 7 days or associated with bleeding requires discontinuation
 - ◆ Any drug-related liver function test (LFT) abnormality that meets the following criteria require discontinuation:
 - Grade ≥ 3 drug-related AST, ALT or Total Bilirubin requires discontinuation.
Note: * In most cases of Grade 3 AST or ALT elevation, study drug(s) will be permanently discontinued. If the investigator determines a possible favorable benefit/risk ratio that warrants continuation of study drug(s), a discussion between the investigator and the BMS Medical Monitor/designee must occur.
 - Concurrent AST or ALT $> 3 \times$ ULN and total bilirubin $> 2 \times$ ULN
- Any Grade 4 drug-related adverse event or laboratory abnormality (including but not limited to creatinine, AST, ALT, or Total Bilirubin), except for the following events, which do not require discontinuation:
 - Grade 4 neutropenia ≤ 7 days
 - Grade 4 lymphopenia or leukopenia or asymptomatic amylase or lipase
 - Isolated Grade 4 electrolyte imbalances/abnormalities that are not associated with clinical sequelae and are corrected with supplementation/appropriate management within 72 hours of their onset
 - Grade 4 drug-related endocrinopathy adverse events such as hyper- or hypothyroidism, or glucose intolerance, which resolve or are adequately controlled with physiologic hormone replacement (steroids, thyroid hormones) or glucose-controlling agents, respectively, may not require discontinuation after discussion with and approval from the BMS Medical Monitor.
- Daratumumab treatment should be permanently discontinued for the following reasons:
 - Grade 4 infusion reactions related to daratumumab.
 - For Grade 3 infusion reactions related to daratumumab: Once reaction symptoms resolve, consider restarting the infusion at no more than half the rate at which the reaction occurred. If the patient does not experience additional symptoms, resume infusion rate escalation at increments and intervals as outlined in **Table 4.3-1**. Repeat the procedure above in the event of recurrence of Grade 3 symptoms. Permanently discontinue daratumumab upon the third occurrence of a Grade 3 or greater infusion reaction
- Any adverse event, laboratory abnormality, or intercurrent illness which, in the judgment of the Investigator, presents a substantial clinical risk to the subject with continued study drug dosing.

- Any event that leads to delay in dosing lasting > 6 weeks for Combo B and C, and > 12 weeks for Combo A from the previous dose requires discontinuation, with the following exceptions:
 - Dosing delays to allow for prolonged steroid tapers to manage drug-related adverse events are allowed.
 - Dosing delays lasting > 6 weeks (Combo A and C) or >12 weeks (Combo A) from the previous dose that occur for non-drug-related reasons may be allowed if approved by the BMS medical monitor.

For Combo A, B, and C, prior to re-initiating treatment in a subject with a dosing delay lasting > 6 weeks (Combo B and C) and > 12 weeks (Combo A), the BMS medical monitor must be consulted. Tumor assessments should continue as per protocol even if dosing is delayed. Periodic study visits to assess safety and laboratory studies should also continue every 6 weeks or more frequently if clinically indicated during such dosing delays.

The assessment for discontinuation of study drug should be made separately considering each study drug. If discontinuation criteria are attributed with only one drug used in this trial, once the subject meets criteria to resume therapy, the subject may continue dosing with the remaining study drug not attributed to criteria for discontinuation. In the nivolumab and BMS-986016 (relatlimab) combination (Combo C), if discontinuation criteria are met, both drugs (nivolumab and BMS-986016) will be discontinued regardless of the assessment of attribution to a particular study drug.

If a subject meets criteria for discontinuation and investigator is unable to determine whether the event is related to both or one study drug, the subject should discontinue all study drugs and be taken off the treatment phase of the study.

Any adverse event, laboratory abnormality, or intercurrent illness which, in the judgment of the Investigator, presents a substantial clinical risk to the participant with continued nivolumab dosing.

4.7.7 Treatment of Study Drug-related Infusion Reactions

Since nivolumab, ipilimumab, and BMS-986016 (relatlimab) contain only human immunoglobulin protein sequences, it is unlikely to be immunogenic and induce infusion or hypersensitivity reactions. However, if such a reaction were to occur, it might manifest with fever, chills, rigors, headache, rash, pruritus, arthralgias, hypo- or hypertension, bronchospasm, or other symptoms. All Grade 3 or 4 infusion reactions should be reported within 24 hours to the BMS Medical Monitor and reported as an SAE if criteria are met. Infusion reactions should be graded according to NCI CTCAE (version 4) guidelines.

For subjects in the combination cohorts A, B and C when ipilimumab or BMS-986016 (relatlimab) are scheduled to be administered on the same day as nivolumab, if a subject has an infusion reaction with nivolumab, the ipilimumab or BMS-986016 (relatlimab) infusion can be given (without prophylactic medications) if the infusion reaction resolves within 3 hours. For scheduling purposes after a nivolumab infusion reaction, the ipilimumab or BMS-986016 (relatlimab) infusion may be given the next day. Prophylactic pre-infusion medications should be given prior to all subsequent nivolumab infusions.

Treatment recommendations are provided below and may be modified based on local treatment standards and guidelines as appropriate:

For Grade 1 symptoms: (Mild reaction; infusion interruption not indicated; intervention not indicated)

- Remain at bedside and monitor subject until recovery from symptoms. The following prophylactic premedications are recommended for future infusions: diphenhydramine 50 mg (or equivalent) and/or paracetamol 325 to 1000 mg (acetaminophen) at least 30 minutes before additional study drug administrations.

For Grade 2 symptoms: (Moderate reaction requires therapy or infusion interruption but responds promptly to symptomatic treatment [eg, antihistamines, non-steroidal anti-inflammatory drugs, narcotics, corticosteroids, bronchodilators, IV fluids]; prophylactic medications indicated for ≤ 24 hours).

- Stop the infusion, begin an IV infusion of normal saline, and treat the subject with diphenhydramine 50 mg IV (or equivalent) and/or paracetamol 325 to 1000 mg (acetaminophen); remain at bedside and monitor subject until resolution of symptoms. Corticosteroid or bronchodilator therapy may also be administered as appropriate. If the infusion is interrupted, then restart the infusion at 50% of the original infusion rate when symptoms resolve; if no further complications ensue after 30 minutes, the rate may be increased to 100% of the original infusion rate. Monitor subject closely. If symptoms recur then no further study drug will be administered at that visit. Administer diphenhydramine 50 mg IV, and remain at bedside and monitor the subject until resolution of symptoms. The amount of study drug infused must be recorded on the electronic case report form (eCRF).

The following prophylactic premedications are recommended for future infusions:

- Diphenhydramine 50 mg (or equivalent) and/or paracetamol 325 to 1000 mg (acetaminophen) should be administered at least 30 minutes before additional nivolumab administrations. If necessary, corticosteroids (recommended dose: up to 25 mg of IV hydrocortisone or equivalent) may be used.

For Grade 3 or Grade 4 symptoms: (Severe reaction, Grade 3: prolonged [ie, not rapidly responsive to symptomatic medication and/or brief interruption of infusion]; recurrence of symptoms following initial improvement; hospitalization indicated for other clinical sequelae [eg, renal impairment, pulmonary infiltrates]). Grade 4: (life-threatening; pressor or ventilatory support indicated).

- Immediately discontinue infusion of study drug. Begin an IV infusion of normal saline, and treat the subject as follows. Recommend bronchodilators, epinephrine 0.2 to 1 mg of a

1:1,000 solution for subcutaneous administration or 0.1 to 0.25 mg of a 1:10,000 solution injected slowly for IV administration, and/or diphenhydramine 50 mg IV with methylprednisolone 100 mg IV (or equivalent), as needed. Subject should be monitored until the investigator is comfortable that the symptoms will not recur. Study drug will be permanently discontinued. Investigators should follow their institutional guidelines for the treatment of anaphylaxis. Remain at bedside and monitor subject until recovery from symptoms.

In the case of late-occurring hypersensitivity symptoms (eg, appearance of a localized or generalized pruritus within 1 week after treatment), symptomatic treatment may be given (eg, oral antihistamine, or corticosteroids).

Guidelines for prevention and management of daratumumab infusion-related reactions

Prevention of Daratumumab Infusion related reactions:

- Pre-infusion medication to be administered to all subjects approximately 1 hour prior to every daratumumab infusion (can be administered before the nivolumab infusion):
 - IV corticosteroid (methylprednisolone 100 mg, or equivalent dose of an intermediate acting or long-acting corticosteroid). Following the second infusion, the dose of corticosteroid may be reduced (methylprednisolone 60 mg IV), PLUS
 - Oral antipyretics (acetaminophen 650 to 1000 mg), PLUS
 - Oral or IV antihistamine (diphenhydramine 25 to 50 mg or Leukotriene Inhibitor (optional) on Cycle 1 Day 1: montelukast 10 mg PO, or equivalent).
- Post-infusion medication to be administered to all subjects to reduce the risk of delayed infusion reactions:
 - Oral corticosteroid (20 mg methylprednisolone or equivalent dose of a corticosteroid in accordance with local standards) on the first and second day after all infusions
 - At the investigator discretion, for subjects with a history of obstructive pulmonary disorder, short and long-acting bronchodilators and inhaled corticosteroids can be administered. Following the first 4 infusions, if subjects experience no major infusion reactions, these additional inhaled post-infusion medications may be discontinued.

Subjects should be carefully monitored for infusion reactions during daratumumab administration. Trained study staff at the clinic should be prepared to intervene in case of any infusion reactions, and resources necessary for resuscitation must be available. All subjects should have blood pressure monitored before and after all infusions. For the first two infusions, blood pressure should also be monitored during the infusion. There will be no dose escalations or reductions of daratumumab allowed. Doses of daratumumab may be interrupted, delayed, or discontinued depending on how well the subject tolerates the treatment.

If an acute infusion reaction is noted, subjects should be managed according to the Investigator's Brochure and as summarized below.

Management of Daratumumab Infusion related reactions:

Per Revised Protocol 06, enrollment and treatment in this cohort have been terminated. Subjects should be carefully observed during daratumumab infusions. Trained study staff at the clinic should be prepared to intervene in case of any infusion reactions, and resources necessary for resuscitation (eg, agents such as epinephrine and aerosolized bronchodilator, also medical equipment such as oxygen tanks, tracheostomy equipment, and a defibrillator) must be available at bedside. Attention to staffing should be considered when multiple subjects will be dosed at the same time.

Interrupt the daratumumab infusion for infusion-related reactions of any severity. Management of infusion reactions may require further reduction in the rate of infusion, or treatment discontinuation of daratumumab.

Subjects who experience adverse events during the infusion must be treated according to the investigator's judgment and best clinical practice. Subjects should be treated with acetaminophen, antihistamine, and/or corticosteroids as needed. Intravenous saline may be indicated. For bronchospasm, urticaria, or dyspnea, subjects may require antihistamines, oxygen, corticosteroids, or bronchodilators. For hypotension, subjects may require vasopressors.

If an infusion is interrupted, then a longer-than-anticipated infusion time may occur. Overnight stays at the hospital because of slow infusion times should not be reported as serious adverse events. However, if the underlying cause of the delayed infusion time is an adverse event or serious adverse event, then that should be reported as such.

Infusion-related reactions of grade 1 or grade 2: Once reaction symptoms resolve, resume the infusion at no more than half the rate at which the reaction occurred. If the patient does not experience any further reaction symptoms, infusion rate escalation may resume at increments and intervals as appropriate as outlined in **Table 4.3-1**.

Grade 3 (severe): Once reaction symptoms resolve, consider restarting the infusion at no more than half the rate at which the reaction occurred. If the subject does not experience additional symptoms, resume infusion rate escalation at increments and intervals as outlined in Table 4.3-1. Repeat the procedure above in the event of recurrence of Grade 3 symptoms. Permanently discontinue daratumumab upon the third occurrence of a Grade 3 or greater infusion-related reaction.

Grade 4 (life threatening): Permanently discontinue daratumumab treatment.

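### Protocol 4.7.7 permits the second antibody after any nivolumab infusion reaction with no grade limit, against 4.7.6 in Combo C and against its own recurrent Grade 2 step

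*Protocol*

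**What the plan says.** Section 4.7.7 addresses Combos A, B and C on days when ipilimumab or relatlimab is due together with nivolumab. After a reaction to nivolumab, the second antibody's "infusion can be given (without prophylactic medications) if the infusion reaction resolves within 3 hours". The next sentence adds: "For scheduling purposes after a nivolumab infusion reaction, the ipilimumab or BMS-986016 (relatlimab) infusion may be given the next day". The paragraph ends: "Prophylactic pre-infusion medications should be given prior to all subsequent nivolumab infusions". Time to resolution is the only condition on same-day dosing. The next-day sentence carries no condition.

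Steps by grade follow in the same section. They are introduced as recommendations that "may be modified based on local treatment standards and guidelines as appropriate". In the Grade 2 step, if symptoms come back after the infusion is restarted, study drug dosing ends for that visit. In the Grade 3/4 step, study drug is stopped for good.

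Section 4.7.6 sets the stop rules:
- For Grade 3: "infusion reaction of any duration requires discontinuation".
- The permanent-stop list also includes "Any Grade 4 drug-related adverse event or laboratory abnormality". Infusion reactions are not among its exceptions.
- In Combo C, once a stop criterion is met, "both drugs (nivolumab and BMS-986016) will be discontinued regardless of the assessment of attribution to a particular study drug".
- In the other combinations each drug is assessed separately, and a drug not held responsible may continue once resume criteria are met. If the "investigator is unable to determine whether the event is related to both or one study drug, the subject should discontinue all study drugs".

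**The concern.** The permission turns on how long the reaction lasts. The stop rule for a Grade 3 infusion reaction says that duration does not matter. The permission names Combo C and relatlimab expressly, yet Combo C is where 4.7.6 stops both antibodies whatever the attribution. No text says which provision takes precedence, and the decision is made at the infusion visit, within hours of the reaction.

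The permission is also silent on two rules that bear on Grade 2 reactions. Section 4.7.3 delays both drugs for Grade 2 non-skin drug-related events other than fatigue until the retreatment criteria are met. Section 4.7.5 requires a subject treated with systemic corticosteroids for a drug-related toxicity to be off them or down to at most 10 mg/day of prednisone equivalent. The Grade 2 step in 4.7.7 allows corticosteroids as treatment.

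What is at stake is subject safety: a second antibody given soon after a reaction that the protocol elsewhere treats as a reason to stop or wait. No endpoint analysis is affected.

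**Working it through.** The documents state no figure on this point, so the check sets the rules side by side.

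| Situation after a nivolumab reaction | 4.7.7 permission, by its letter | Other rule | Result |
|---|---|---|---|
| Combo C, Grade 3 or 4 | Relatlimab allowed the same day if resolved in 3 hours, or the next day | 4.7.6: both drugs stop, whatever the duration or attribution | Contradiction |
| Combos A, B, C, recurrent Grade 2, same visit | Second antibody allowed if resolved in 3 hours | 4.7.7 Grade 2 step: no more study drug at that visit | Contradiction within one section |
| Combos A, B, C, recurrent Grade 2, next day | Allowed | The Grade 2 step covers that visit only | No clear contradiction, unless the event is graded 3 |
| Combos A, B, C, Grade 2 treated with corticosteroids | Allowed | 4.7.3 delay and 4.7.5 corticosteroid criterion | Not cited; interaction unstated |
| Combos A and B, Grade 3 or 4 | Allowed | 4.7.6: per-drug attribution, then resume criteria; all drugs stop if attribution is unclear | Not a demonstrated contradiction |

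Two details matter for the second row. Sections 4 and 4.1 count both antibodies as investigational product in Combos A, B and C, so study drug in the Grade 2 step covers the second antibody. The Grade 3 description in 4.7.7 includes symptoms returning after initial improvement, so a recurrent Grade 2 reaction may have to be graded 3.

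**Size.** Inputs: planned cohort sizes from Protocol 8.1, and nivolumab infusion-reaction rates from Protocol 1.5 (severe, below 1% of subjects; any grade, 1% to 6%). Assumptions: the nivolumab rates hold in the combinations, and severe means Grade 3 or higher.

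- Combo C, severe: 40 × (<1%) = fewer than 0.4 subjects. This is an upper bound. Enrollment closed at Revised Protocol 05 (18-Apr-2018), Appendix 5 calls accrual low, and treatment is capped at 24 months. Under the current version (07-May-2019) only subjects still on treatment are exposed.
- Recurrent Grade 2: the documents give no rate, so no count is possible. Recurrences graded 3 already sit inside the severe rate, and those graded 2 inside the any-grade rate.
- Any grade, for context. Planned total: Combo A 5 × 40 = 200; Combo B 110 + 40 = 150; Combo C 40; sum 390. Removing the closed anogenital (80) and Combo C (40) cohorts leaves 390 − 120 = 270. The range is 270 × 1% = 2.7 to 390 × 6% = 23.4 subjects.

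The any-grade range is not a count of subjects at risk. It includes Grade 1 reactions, after which giving the second antibody is unobjectionable. The rates are per subject over a whole course, whereas in Combo A only one nivolumab visit in three is also an ipilimumab visit (every 6 weeks against every 2), and in Combo B only the first 4 doses pair the two drugs.

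**The case against.** The strongest reply is that 4.7.7 has grade rules directly below the permission. A site reading that section alone meets a permanent stop for Grade 3/4 and a same-visit stop for recurrent Grade 2. The permission is permissive and 4.7.6 is mandatory, so withholding satisfies every rule at once. The sentence on premedicating later nivolumab infusions presumes that nivolumab continues, which points to lower grades. Grade 3/4 reactions go to the Medical Monitor within 24 hours.

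Most of this stands, and it limits the point to a risk of misreading. It does not remove it. The graded steps may be modified locally, the permission does not cite them, and the Grade 3/4 sentence can be read as stopping only the drug being infused.

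Some stronger readings are tempting but not supported:
- *That section 4.3 is contradicted.* It starts the second infusion after the patient has been watched and found free of a reaction, with a 60-minute limit for relatlimab. This reads naturally as the routine visit, with 4.7.7 as the exception. Only a cross-reference is missing.
- *That Grade 3/4 in Combos A and B conflicts with 4.7.6.* Per-drug attribution there can allow ipilimumab later. A subject just given the methylprednisolone 100 mg IV recommended for Grade 3/4 would also be hard to call eligible under 4.7.5 that day.
- *That 4.7.3 and 4.7.5 are contradicted at Grade 2.* Both apply without being repeated, same-day dosing already requires resolution, and corticosteroids are optional at that grade.
- *That next-day dosing after recurrent Grade 2 is barred.* The step covers that visit only.

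**Conclusion.** The point holds as an inconsistency in the dosing rules. By its letter, the 4.7.7 permission contradicts 4.7.6 for Grade 3/4 reactions in Combo C and the recurrent Grade 2 step for same-visit dosing in Combos A, B and C. It also leaves its relation to 4.7.3 and 4.7.5 unstated.

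The size is small. The Combo C bound of fewer than 0.4 subjects rests on planned enrollment and on the nivolumab rate carrying over to the combination; actual exposure is lower. The recurrent Grade 2 frequency is unknown. A reader might infer from the any-grade range that up to about 23 subjects are at risk, or that 4.7.7 has no grade rule at all; neither is supported. Severity: minor. Confidence is high that the permission sentences carry no grade limit, but the documents do not show that any site would dose against a stop rule.

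**What to change.** In 4.7.7:
- Limit both the same-day and next-day permissions to Grade 1 and non-recurrent Grade 2 reactions that have resolved and meet 4.7.5, including its corticosteroid criterion. Make them expressly subject to 4.7.3 and 4.7.6.
- State that after recurrent Grade 2 symptoms no second antibody is given at that visit, and that the Grade 3 rule applies if the event is graded 3.
- State that after Grade 3/4 relatlimab is not given in Combo C, and that in Combos A and B ipilimumab is given later only under the 4.7.6 attribution rule and 4.7.5.

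In 4.3, add a cross-reference saying that the no-reaction check and the 60-minute relatlimab start describe the routine visit and that 4.7.7 governs after a reaction.

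The cost is a few sentences in a protocol revision and no new tests. A few subjects in Combos A and B may need a separate ipilimumab visit.
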